Complete Title: Online Randomized Experiment Evaluating Ultra-Processed Food Warning Labels on Social Media Posts Among Teens and Young Adults

Short Title: Effects of UPF Warning Labels on Social Media Among Teens and Young Adults

Protocol Date: August 25, 2025

NCT #: NCT07227519

Study Principal Investigators:

[name]

University of Tennessee Health Science Center

Email: [contact]

[name]

Stanford University

Email: [contact]

Introduction

The goal of the analyses described here is to use data collected through an online randomized experiment to examine teens' and young adults' responses to ultra-processed food (UPF) warning labels on social media posts. These analyses assess the effect of a highly visible UPF warning label displayed beneath social media posts, compared to a control condition with no label, on consumer understanding and purchase intentions. This analysis plan pre-specifies the analyses before collecting data and therefore serves as our ex-ante planned analysis.

Study Protocol

Participants will complete an online randomized experiment. After providing informed consent, they will be randomized to one of two trial arms: (1) UPF warning labels or (2) no-label control. Participants will view four social media posts (presented in random order; all feature UPF) based on real Instagram posts from leading food and beverage companies. Labels will be shown according to participants' assigned trial arm. Participants will then respond to survey questions assessing consumer understanding, purchase intentions, perceived healthfulness, perceptions of control over healthy eating, and policy support for ultra-processed food warning labels. At the end of the UPF survey, participants will also answer an open-ended question on their understanding of the term "ultra-processed food."

Statistical Considerations

General Principles

We will use a two-sided critical alpha of 0.05 for all statistical tests. All confidence intervals will be two-sided and set at the 95% level. Analyses will be conducted on an intent-to-treat basis and will not be adjusted for any covariates, given the randomized design. Missing data will be handled in linear mixed models through maximum likelihood estimation (assumes missing at random [MAR]). Given the exploratory nature of the study, we will not adjust p-values for multiple comparisons.

Primary Outcome

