- a. We will use the same model from 2b to evaluate the effects of UPF warning labels on perceived healthfulness. Perceived healthfulness will be regressed on trial arm (warning label vs. control), and we will estimate and report the average perceived healthfulness for each group, as well as the ADE.
- b. We will describe the percentage of participants (pooled across trial arms) who report increased control over healthy eating. Similarly, we will describe the percentage of participants who report supporting requiring UPF warnings. We will additionally describe these percentages stratified by age group (teens vs. young adults) and gender (male vs. female).

4. Exploratory Analysis:

- a. We will use chi-square tests to compare the distribution of UPF understanding categories (low/moderate/high) between trial arms. If the distributions do not differ significantly, we will proceed to test participants' understanding of the term "ultra-processed food" as a moderator in section 4b. This step is to make sure that being exposed to the warning labels does not influence their understanding of the term.
- b. We will examine whether participants' understanding of the term "ultra-processed food" moderates the effect of the label on consumer understanding, purchase intention, perceived healthfulness, perceptions of control over healthy eating, and policy support for UPF warning labels. Moderation will be tested by adding UPF understanding and its interaction with trial arm to the mixed models described in sections 2 and 3. If interactions are significant, we will report stratified effects.

5. Additional considerations and sensitivity analyses:

- a. If models fail to converge for the repeated measures (unlikely), we will test simpler covariance structures.
- b. For repeated measures, we will additionally add fixed effects for social media posts in the mixed models to adjust for any systematic differences across the social media posts.

- c. For consumer understanding (binary), we will conduct sensitivity analyses using Poisson GEE models with a log link (to estimate risk ratios for consumer understanding) and robust standard errors.

Sample Size Needs

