We plan to collect data from 1,000 participants. With 80% power and a two-sided alpha of 0.05, we can detect an effect size of approximately Cohen's $d = 0.18$ for non-repeated-measures outcomes. For repeated measures, assuming four repeated measures per participant, the minimal detectable d is approximately 0.13–0.16, assuming within-person correlation $\rho=0.4–0.7$. These represent small effect sizes, but ones that are meaningful at the population level.

Exclusions and Outliers

We will exclude participants who complete the survey implausibly quickly (defined as completing in less than one-third of the median completion time).

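### The SAP calls its analyses intent-to-treat but excludes randomized participants on completion time, and no planned analysis includes them

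*SAP*

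**What the plan says.** General Principles gives the analysis basis without qualification: "Analyses will be conducted on an intent-to-treat basis and will not be adjusted for any covariates, given the randomized design". The Study Protocol section fixes the order of events. Randomization follows consent: "After providing informed consent, they will be randomized to one of two trial arms: (1) UPF warning labels or (2) no-label control". The four posts come next, and the outcome questions after them: "Participants will then respond to survey questions assessing consumer understanding, purchase intentions, perceived healthfulness".

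Exclusions and Outliers then removes people from that randomized group: "We will exclude participants who complete the survey implausibly quickly (defined as completing in less than one-third of the median completion time". It does not say whether the median is pooled or taken within arm, or when the clock starts.

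On incomplete data, General Principles says: "Missing data will be handled in linear mixed models through maximum likelihood estimation". The additional analyses in Statistical Methods section 5 are a fallback for convergence (5a: "If models fail to converge for the repeated measures (unlikely), we will test simpler covariance structures"), an adjustment for post (5b: "For repeated measures, we will additionally add fixed effects for social media posts in the mixed models") and a Poisson GEE for the binary outcome (5c). The SAP defines no separate analysis set.

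**The concern.** Intent-to-treat keeps the groups as randomization made them. Once people are dropped on something observed after assignment, that protection is no longer automatic. A label gives participants something more to read, so it may slow some of them, and a fast responder in the control arm might have stayed above the cut-off with the label. The two retained groups could then differ in kind.

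Two separate things are at stake. First, the retained-set effect answers a different question: the effect among people who were not excluded. Second, if the label changes who is excluded, the comparison within the retained set carries some selection. A report that follows this plan would call the result intent-to-treat, and no pre-specified analysis would show whether the exclusion mattered. It touches every outcome, including both primary ones.

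**Working it through.** **Do the statements fit together?** Randomization comes before the posts and the outcome questions. Wherever the clock starts, completion time is known only once the survey is finished, after assignment. A rule based on it removes randomized people, so the set is not everyone randomized.

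**Does anything planned bring them back?** 5a changes the covariance structure, 5b adds post effects, and 5c changes the model and the effect measure. None changes who is analysed. Maximum likelihood deals with unanswered items among people in the data set, not with people removed by rule.

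**The SAP's own precision figures.** Inputs from Sample Size Needs: 1,000 participants, 80% power, two-sided alpha 0.05, four measures, rho 0.4 to 0.7. Equal allocation (500 per arm) is assumed, since the ratio is not stated.
- Single measure: d = (1.96 + 0.84) × sqrt(2/500) = 0.177 (SAP: about 0.18).
- Repeated measures: multiply by sqrt((1 + 3·rho)/4), which gives 0.131 and 0.156 (SAP: 0.13 to 0.16).
- The same factor gives the standard error of the risk difference at an assumed 50% correct: (2 × 0.5/sqrt(1000)) × sqrt((1 + 3·rho)/4) = 2.35 points (rho 0.4) to 2.78 points (rho 0.7).

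These figures reproduce and are not in dispute. The standard error serves as a yardstick.

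**Illustration of size.** All further inputs are assumptions:
- Completion times are log-normal with log-SD 0.6 or 0.8, and the label lengthens time by a share s of 0 to 20%.
- The cut-off is one-third of the pooled median.
- The label effect is D = 10 points in non-speeders and zero in speeders.
- Speeders are g points less often correct than unlabelled non-speeders.
- People whom the label slows past the cut-off still answer like speeders.

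On the log scale the pooled median m solves 0.5·Φ(m/SD) + 0.5·Φ((m − ln(1+s))/SD) = 0.5, and the cut-off is c = m − ln 3. The excluded shares are e0 = Φ(c/SD) in control and e1 = Φ((c − ln(1+s))/SD) with the label.
- All-randomized effect: (1 − e0)·D.
- Retained-set effect: [(1 − e0)·D − (e0 − e1)·g]/(1 − e1).
- Their difference splits into a change of estimand, e0·D, and differential exclusion, −(e0 − e1)·(D + g)/(1 − e1).

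Results for g = 20 to 50 points:

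| log-SD | s | e0 vs e1 | Estimand part (points) | Differential-exclusion part (points) |
|---|---|---|---|---|
| 0.6 | 0% | 3.35% both | +0.34 | 0 |
| 0.6 | 5% | 3.67% vs 3.06% | +0.37 | -0.19 to -0.38 |
| 0.6 | 20% | 4.66% vs 2.37% | +0.47 | -0.70 to -1.41 |
| 0.8 | 0% | 8.48% both | +0.85 | 0 |
| 0.8 | 5% | 8.97% vs 8.02% | +0.90 | -0.31 to -0.62 |
| 0.8 | 20% | 10.40% vs 6.85% | +1.04 | -1.14 to -2.29 |

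The total runs from -1.25 points (last row, g = 50) to +0.85.

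**Sensitivity to how speeders answer**, at s = 20%:
- Random clicking among three options gives about 33% correct. Against 50% that is g of about 17 points, and the total is -0.16 (log-SD 0.6) or +0.02 (0.8).
- All posts feature ultra-processed food and only Yes is coded correct. Speeders who always click Yes are 100% correct, so g = -50. At log-SD 0.8: 1.04 − 3.55 × (0.10 − 0.50)/0.9315 = 1.04 + 1.52 = +2.56 points.
- If slowed people instead answer like non-speeders, the retained effect is exactly D and the total is e1·D − (e0 − e1)·g. At log-SD 0.8 this is 0.69 − 1.78 = -1.09 for g = 50 and 0.69 + 1.78 = +2.46 for g = -50.

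The extremes are 1.25/2.78 = 0.45 to 1.25/2.35 = 0.53 of a standard error downwards, and 2.56/2.78 = 0.92 to 2.56/2.35 = 1.09 upwards.

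**The case against.** The strongest defence is that speed exclusions are ordinary quality control in online surveys. This one is numeric, pre-specified, stated once for everyone and blind to the answers. Intent-to-treat can also be read narrowly as analysis by assigned arm, which the plan honours, and the SAP never promises a full-set run. Much of this stands: the rule is legitimate and may remain primary. But the narrow reading does not rescue the label, because the phrase is unqualified and a reader would take it to mean that everyone randomized is analysed.

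A second objection is that the timed part may exclude the viewing of posts, or may begin before randomization. This is fair. The text does not establish that the time includes label exposure, only that it is known after assignment and could be influenced by the label.

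A reader might infer that the primary results will be materially biased, or that the label's effect will be understated. The documents do not support either: they give no completion times or exclusion rate, and the sign reverses with how speeders answer. Nor is half a standard error a ceiling.

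A reader might also cite section 4a, which checks an exploratory moderator across arms: "This step is to make sure that being exposed to the warning labels does not influence their understanding of the term". It shows awareness of influence after exposure, but it does not govern data-quality exclusions. The lack of a similar check on completion time is not in itself an error in the SAP.

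**Conclusion.** The point holds, as a mismatch between label and analysed set together with a missing full-set analysis. Confidence in both is high, since they rest on the SAP's text alone. The size and direction of any effect are unknown. The illustrative range of about -1.3 to +2.6 points rests wholly on the assumed time distribution, label delay, effect size and answering behaviour, and it is not a bound. If exclusion is equal across arms and removes the same kind of person in each, no selection remains and only the change of estimand is left. The matter should be corrected, but it is not a demonstrated threat to the primary conclusions.

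**What to change.** Choose one of two options; either removes the contradiction.
1. Make all randomized participants with outcome data the intent-to-treat set for the analyses.
2. Keep the speed exclusion as primary, call the set modified intent-to-treat, and add to section 5 a re-run of models 2a and 2b on all randomized participants with outcome data.

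In addition, state under Exclusions and Outliers that the cut-off uses one median pooled over arms and computed without regard to outcomes, so that everyone faces the same threshold. Listing the number excluded in each arm would help readers, though its absence is not a fault of the SAP.

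The cost is a corrected label, a sentence on the median and one extra run of models already specified, on data already collected. The downside is that careless responders may slightly dilute a full-set estimate: by e0·D, or 0.3 to 1.0 points under the assumptions above, if the label has no effect in speeders.
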